The DSMB for this study met on 12 OCT 2020 to review preliminary dose comparison data. It was determined that the 100 mg twice daily dose showed a trend for amelioration of FVC loss and recommended all patients in Part B be treated with the 100 mg twice daily dose. Therefore, all patients who participate in Part B after the implementation of this amendment will be treated with the 100 mg twice daily dose. Any patients already participating in Part B on the 50 mg once daily dose will be converted to the 100 mg twice daily dose regimen. Patients will have monthly telephone assessments and quarterly in-clinic assessments. All patients that complete the study visits through Part B will have the option to continue receiving AP01 by enrolling or planning to enroll in the AP01-005 study or to stop dosing after the EOS/Visit 12 and return for a Follow-up visit, 28 days after their End of Study visit.

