## 5.3. Study Restrictions

Patients are not to receive pirfenidone or nintedanib within 3 days prior to randomization to the study and during participation in Part A of the study. Nintedanib, but not oral pirfenidone, use is allowed if deemed necessary by the investigator during Part B of the study. In the event of an acute exacerbation, any treatment deemed necessary by the investigator is acceptable until the resolution of the event. Other than brief periods of medically appropriate treatment for acute IPF exacerbation, patients will not receive any other therapy for the treatment of IPF during Part A. If in the opinion of the investigator, a patient is in need of treatment with oral pirfenidone or nintedanib during Part A, the patient should be discontinued from the study and return to the clinic for their Early Termination visit. Oxygen use is allowed during the study.

Avalyn Pharma, Inc.  
AP01-002

Protocol v2.1  

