The primary endpoint of interest for efficacy is the absolute change from Baseline to Week 24 in FVC % predicted. Linear mixed-effects models will be used to estimate slopes representing the mean change from Baseline to Week 24 in each treatment group, and the difference between treatment groups will be examined. Baseline FVC % predicted, region, age at screening, sex, baseline D_{LCO} % predicted, and baseline progression-related biomarker (CXCL13, CCL18, MMP3) values each categorized as >Median level vs. ≤Median level will be included as covariates in the model. Similar modeling strategies will be employed for longer-term data obtained from Part B of the study.

No control group is included in this study; however, there is ample data in the literature showing a consistent rate of decline in IPF patients not receiving anti-fibrotic therapies. Historical data from the placebo groups of the three Phase III clinical trials of oral pirfenidone (ASCEND and CAPACITY trials) showed an average decline in FVC % predicted of ~4% at 6 months. These results will be used as a historical comparator. For each AP01 treatment group, a one sample Wald test will test H_0 : mean change from Baseline to Week 24 in FVC % predicted $\leq -4\%$ vs H_1 : mean change from Baseline to Week 24 in FVC % predicted $> -4\%$. For each AP01 treatment group, a 95% one-sided confidence interval will be derived for the difference (between A01 and historical reference) in the mean change from Baseline to Week 24 in FVC % predicted. Additionally, we will compare the change from baseline in FVC % predicted at Week 24 for each treatment group to the average decline in FVC % predicted at 24 weeks for patients with no documented antifibrotic treatment calculated from a set of (1) Pulmonary Fibrosis Foundation (PFF) Registry patients and (2) Australian IPF Registry patients, with matching baseline characteristics. For each treatment group and each registry, a two-sided Wald test will test: H_0 : 24-week $FVC\ decline_{AP01\ group} = 24\text{-week}\ FVC\ decline_{registry}$ vs. H_1 : 24-week $FVC\ decline_{AP01\ group} \neq 24\text{-week}\ FVC\ decline_{registry}$. For each of the 2 AP01 treatment groups and for each of the 2 registries, a 95% two-sided confidence interval will be derived for the difference (between AP01 and registry) in the mean change from Baseline to Week 24 in FVC % predicted.

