8.1. Primary Efficacy Endpoint and Analysis

Spirometry will be conducted at approximately the same time each visit (within 60 minutes of Day 1 spirometry measurement) with the patient in seated position. The test will be performed to American Thoracic Society/European Respiratory Society (ATS/ERS) guidelines³. On days of clinic visits (including the screening visit), patients must refrain from strenuous activity at least 12 hours prior to pulmonary function testing (PFT). FVC % predicted will be calculated using the ERS Global Lung Function Initiative 2012 equations² as outlined in the clinical study manual.

PFTs will be collected at Screening, Baseline and at each post-Baseline time point (Week 4, 8, 12, 16, 20, 24, 36, 48, 60, 72 and Follow-Up) as described in Section 6.1.

The primary efficacy endpoint is the change from baseline in absolute FVC % predicted from Baseline to Week 24. The population used for efficacy analyses of the primary variable will be the PP with the FAS used for the first sensitivity analyses.

A linear mixed-effects model (PROC MIXED) will be used and differences between treatment groups between slopes estimating the change from baseline in absolute FVC % predicted from Baseline to Week 24 will be examined. Baseline FVC % predicted, region, age at screening, sex, baseline DL_{CO} % predicted, and baseline progression-related biomarker (CXCL13, CCL18, MMP3) values each categorized as >Median level vs. ≤Median level will be included as covariates in the model. This analysis requires at least three post-baseline FVC % predicted values in addition to baseline be available for a patient to be included in the analysis so that the slope estimated is identifiable. Similar modeling strategies will be employed for longer-term data obtained from Part B of the study. Spirometry data collected after patients switched dosing regimen from 50 mg once daily to 100 mg twice daily will be omitted for this analysis.

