Patients will obtain spirometry readings at home on the same day and at approximately the same time each week (+/- 2 hours). Home spirometers will be dispensed at the Baseline visit; patients will be trained on the use of home spirometers prior to their departure from the Baseline visit. Home spirometer training and accountability data will be presented in a listing.

The home spirometry measurements (FVC, FVC % predicted) will be summarized by treatment group and visit including change from the baseline in-clinic pre-dose spirometry value using descriptive statistics. For the tabular summary and graphical summary, biologically implausible values and outliers will be removed as described previously in Section 8.1. The remaining spirometry measurements (FVC, FVC % predicted) within the mapping window for a scheduled visit will be averaged. All home spirometry data will be included in a listing.

Bland-Altman plots will be produced to describe the agreement between the home and in-clinic spirometry measurements at each visit. In these plots, the average of home spirometry measurements within the mapping window for a scheduled visit will be compared with the in-clinic spirometry at each visit.

A linear mixed-effects model (PROC MIXED) approach¹² will be used to determine the repeated-measures correlation coefficient estimates for in-clinic FVC measurements with averages of home FVC measurements across visits for each treatment group. A normal approximation will be used to determine the estimate for the correlation coefficient (ρ_{hat}), the 95% confidence intervals for the correlation coefficient estimate and p-value. This analysis for Part B will only use measurements in the 50 mg once daily group taken prior to the switch to the 100 mg twice daily group if the patient switched dosing regimens.

9.2. Change in absolute FVC % predicted from home spirometry Baseline visit to Week 24 and Week 72

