A linear mixed-effects model (PROC MIXED) will be used for analysis. The model will include FVC % predicted (measured at home) as the dependent variable and will include patient and time of spirometry reading (study day) as random effects, and fixed effects of treatment group, time of spirometry reading (study day), along with a treatment-by-time interaction. Longitudinal plots at selected timepoints displaying the model adjusted, least square means and 95% confidence intervals will be produced. Spirometry data collected after patients switched dosing regimens from 50 mg once daily to 100 mg twice daily will be omitted for this analysis.

9.3. Correlation of extent of fibrosis and lung volume as measured by HRCT at Baseline and Week 24 to other measures of clinical status

The following HRCT measurements will be correlated with the following In-Clinic Spirometry Measurements (FVC) at Baseline and Week 24 or early termination:

- Extent of Fibrosis as Measured by HRCT with FVC

This document is confidential.

Statistical Analysis Plan

Sponsor: Avalyn Pharma, Inc.; Protocol No.: AP01-002

- Lung Volume as Measured by HRCT with FVC.
- Change in Extent of Fibrosis as Measured by HRCT with Change in FVC
- Change in Lung Volume as Measured by HRCT with Change in FVC

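### In the longer-term FVC comparison the 50 mg slope stops at the dose switch while the 100 mg slope runs to Week 72, so part of any common change in decline after Week 24 enters the estimated dose difference

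*SAP*

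**What the plan says.** SAP Section 8 sets the model: "Linear mixed-effects models will be used to estimate slopes representing the mean change from Baseline to Week 24 in each treatment group". SAP 8.1 extends it to Part B: "Similar modeling strategies will be employed for longer-term data obtained from Part B of the study". It then adds the omission rule: "Spirometry data collected after patients switched dosing regimen from 50 mg once daily to 100 mg twice daily will be omitted for this analysis". Pulmonary function is measured at "Week 4, 8, 12, 16, 20, 24, 36, 48, 60, 72 and Follow-Up", and no cut-off is stated for patients randomised to 100 mg.

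SAP 9.2, headed "Change in absolute FVC % predicted from home spirometry Baseline visit to Week 24 and Week 72", fits home FVC % predicted on study day by treatment group and has the same rule: "Spirometry data collected after patients switched dosing regimens from 50 mg once daily to 100 mg twice daily will be omitted for this analysis".

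The switch comes from the DSMB meeting of 12 October 2020. The protocol synopsis (Study Overview/Design) says: "Any patients already participating in Part B on the 50 mg once daily dose will be converted to the 100 mg twice daily dose regimen". Later entrants to Part B receive 100 mg twice daily. SAP 6.1 allows for 50 mg patients who never switched, and SAP 7.1 will summarise switch timing, but neither document gives the times.

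Protocol 5.3 bars nintedanib in Part A and then relaxes this: "Nintedanib, but not oral pirfenidone, use is allowed if deemed necessary by the investigator during Part B of the study".

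SAP 8.1 ends with a second longer-term FVC model. It keeps post-switch data, treats regimen as time-varying and also uses continuous time.

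**The concern.** With one straight line per arm, the 50 mg slope describes decline from baseline to the switch, and the 100 mg slope describes decline from baseline to Week 72. The two are comparable only if the underlying rate is constant for 72 weeks. If the rate changes after Week 24 in both arms for a reason unrelated to AP01 dose, the 100 mg line absorbs more of the change than the 50 mg line, and the treatment-by-time term picks up the gap. Nintedanib being allowed only from Part B is one such reason that the documents themselves supply.

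At stake is the longer-term estimate of the regimen difference and its confidence interval. Comparing the regimens to guide later studies is a stated objective (Protocol Section 2; SAP 3.2). For 50 mg patients who switched, a fitted Week 72 value under SAP 9.2 would also be an extrapolation beyond any reading on 50 mg.

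**Working it through.** **Inputs from the documents.** 50 per arm and SD 4.5 for the change in FVC % predicted; declines of 1.5 (oral pirfenidone) and 3.9 (placebo) at Week 26 (Protocol 11.1; SAP 3.5); the clinic visits of SAP 8.1.

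**The plan's own figures.** Half-width of the 95% CI: 1.96 × 4.5/√50 = 1.25, as stated. The stated power of around 75% is reproduced if the arm difference is 3.9 − 1.5 = 2.4, which is an inference because the documents do not give the effect behind it. SE = 4.5 × √(2/50) = 0.90, 2.4/0.90 = 2.67, and power = Φ(2.67 − 1.96) = 0.76.

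**Assumptions.** Both arms follow the same true path: rate r per 24 weeks to Week 24, then m × r. Random intercept and slope; residual SD 2.0. Slope SD = √(4.5² − 2 × 2.0²) = 3.5 per 24 weeks, so that the Week 24 change has SD 4.5. The Week 26 declines serve as rates per 24 weeks. Switch times are assumed.

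**Share that leaks when everyone switches at Week 24.** Write t = week/24. The common path departs from a straight line by (m − 1) × r × max(t − 1, 0). The 50 mg line (Weeks 4 to 24) sees none of this. The 100 mg line picks up the slope of max(t − 1, 0) on t over its ten visits:

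- mean t = 12.5/10 = 1.25
- Sxx = 24.03 − 10 × 1.25² = 8.40
- Sxy = 12.5 − 12.5 × 5/10 = 6.25
- share = 6.25/8.40 = 0.744

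SE of the slope difference: slope variance per patient is 12.25 + 4/8.40 = 12.73 (100 mg) and 12.25 + 4/0.486 = 20.48 (50 mg), so √((12.73 + 20.48)/50) = 0.815.

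For weekly home readings, treated as continuous over t from 0 to 3, the same ratio is (14/9 − 1.5 × 2/3)/0.75 = 0.74.

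**Other switch patterns, same model.** False difference is 100 mg minus 50 mg, in points per 24 weeks, when the rate halves after Week 24. It equals share × 1.95 for r = −3.9 and share × 0.75 for r = −1.5.

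| Switch times | Share | r = −3.9 | r = −1.5 | SE as planned | SE with common knot |
|---|---|---|---|---|---|
| All at Week 24 | 0.74 | +1.45 | +0.56 | 0.815 | 0.889 |
| 50/25/25% at Weeks 24/36/48 | 0.47 | +0.92 | +0.36 | 0.770 | 0.796 |
| Even over Weeks 24 to 72 | 0.23 | +0.44 | +0.17 | 0.738 | 0.743 |
| All at Week 48 (bounding case) | 0.20 | +0.39 | +0.15 | 0.728 | 0.732 |

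If the rate rises by half, the signs reverse. If it is constant (m = 1), the difference is 0. Residual SDs from 1.0 to 3.0 leave the all-at-Week-24 bias unchanged.

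For r = −3.9 and a halved rate, a nominal two-sided 5% test would reject in 43%, 22%, 9% and 8% of trials, row by row. These rates only show the bias relative to its SE.

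**Rates from the documents' own figures.** Set Week 26 of ASCEND (Protocol 11.1) beside Week 72 of CAPACITY 2 (Protocol 1.2.2).

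- Oral active: 1.5 × 24/26 = 1.38 early, (8.0 − 1.5) × 24/46 = 3.39 later. The change of about 2.0 gives 0.46 (share 0.23) to 1.49 (share 0.744) against 100 mg.
- Placebo: 3.9 × 24/26 = 3.60 early, (12.4 − 3.9) × 24/46 = 4.43 later. The change of about 0.83 gives 0.19 to 0.62 against 100 mg.

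These cross two trials, so they are indicative only.

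**The time-varying model in SAP 8.1.** With r = −3.9 and a halved rate, its false difference is +1.64 (all at Week 24), +0.89 (50/25/25%) and +0.52 (even). Keeping the post-switch data does not cure the problem while time is linear.

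**Repairs.** In the slope model, a common Week 24 knot, common visit effects, or cutting both arms at Week 24 each gives a false difference of 0.00 for every m from 0 to 2.

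**The case against.** The strongest reply has four parts.

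- **No between-arm test.** SAP 6.1 plans no formal hypothesis tests, and the Wald tests in SAP Section 8 compare each group with historical or registry decline at Week 24. This stands: the harm is to an estimate and its interval, and a reader should not infer an inflated type I error for a planned test.
- **Linear time is inferred.** SAP 8.1 says only that Part B modelling will be similar. This stands for the slope model, though SAP 9.2 names study day and the second SAP 8.1 model names continuous time.
- **Decline may be close to linear.** SAP Section 8 describes untreated decline as consistent, and the placebo figures above change by only about 0.83 points per 24 weeks. This limits the likely size. It does not cover treated patients who may add nintedanib. Nor is nintedanib confined to 100 mg: 50 mg patients in Part B before conversion may also take it.
- **Other displays expose the switch.** SAP 6.1 has separate groups for those who stayed and those who switched, with spider plots. These help a reader see the unequal windows, but they are descriptive and leave the model estimate uncorrected.

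It is tempting to infer that all of any later change would be read as a dose effect, or that the error must favour 100 mg. Neither follows. Only a share leaks in, and the sign depends on whether decline slows or speeds up. The documents' own cross-trial figures point, if anything, to acceleration, which would count against 100 mg. Nor do the documents say that this analysis supports the regimen choice, which the DSMB made on preliminary 6-month data before this SAP (15 July 2021).

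**Conclusion.** The point holds for the longer-term between-regimen models in SAP 8.1 and 9.2. About a quarter to three quarters of a common post-Week-24 change in decline enters the dose contrast of the slope model. The exact share depends on switch times that the documents do not give, and patients who stayed on 50 mg in Part B reduce it. For a 2-point change this is about 0.46 to 1.49 points per 24 weeks, against a planned SE of roughly 0.74 to 0.82.

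The conclusion assumes linear time in Part B and a rate change shared by both arms. With constant decline there is no bias. The Baseline to Week 24 primary comparison is not touched, because no one switches before Part B. This is worth correcting because the correction is cheap; it does not threaten the main result.

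**What to change.** In the longer-term between-regimen models of SAP 8.1 (including the time-varying model) and SAP 9.2, do one of the following:

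1. Add a time term common to both arms: a knot at Week 24, or categorical visit effects. The knot suits the study-day model in 9.2. Visit effects allow any common path, not only a bend at Week 24.
2. Limit the between-arm slope contrast to the period both arms share, Baseline to Week 24.

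In either case, report Week 72 results within arm for patients randomised to 100 mg, and give no 50 mg estimate beyond the last observed 50 mg reading.

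Cutting 100 mg patients at the date the amendment took effect at their site might look like a matching rule, but it is not one. 50 mg patients still in Part A on that date stay on 50 mg until they enter Part B, so the windows would still differ.

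The cost is SAP wording and some precision. If everyone switched at Week 24, the SE of the slope difference rises from about 0.82 to 0.89 (knot) or 0.91 (visit effects, or both arms cut). With spread-out switching the increase is smaller. The time-varying model also loses some precision. A common time term does not correct for nintedanib use that differs between arms.

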#### **5.6. Patient Withdrawal Criteria**

Patient participation in the study is purely voluntary; patients can withdraw consent at any time for any reason without effect on subsequent care. This is an open-label study in which the investigator is aware of the patient's treatment assignment. The investigator, in consultation with the Medical Monitor, or the Medical Monitor may exercise his or her medical judgment to terminate a patient's participation in the study due to clinically significant changes in any clinical or laboratory parameter. If in the opinion of the investigator, the patient is failing the study drug for lack of efficacy, as evidenced by an excessive decline of FVC, during Part A of the study, the patient can be withdrawn and placed on alternative therapies. During Part B of the study, the investigator may choose to add nintedanib, but not oral pirfenidone, to the patient's treatment regimen.

Any randomized patient desiring to discontinue prior to study completion should be encouraged to discuss his or her reasons and concerns with the investigator. If, after discussion, the patient still chooses to discontinue participation in the study, the patient should be encouraged to attend an Early Termination visit. (Patients that discontinue during the screening process will be considered screen failures.) Patients who are discontinued during a scheduled visit will be encouraged to complete all unique assessments for both that study visit and the End of Treatment visit at the time of discontinuation. If a patient is still participating in Part A and has had a HRCT scan within the past month, the HRCT from the End of Treatment visit will not be performed.

An End of Study case report form (CRF) page will be completed for every patient who receives study medication whether or not the patient completes the study. The reason for any early discontinuation from the study will be indicated on this form. The primary reason for any early termination will be selected from the following standard categories:

- Adverse Event: Clinical or laboratory events occurred that in the medical judgment of the investigator, in consultation with the Medical Monitor and Avalyn Pharma, represents an unacceptable risk to the patient if he/she continues in the study. This includes serious and non-serious AEs regardless of relationship to study medication. The investigator must follow the patient until the AE resolves or satisfactorily stabilizes

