12 OCT2020

### **8.3.5. Packaging and Labeling of AP01 and Nebulizer Kits**

#### AP01 IP Supply

Overwrapped AP01 IP ampoules will be packaged and labelled as required by regional regulation by PPD Development, L.P. in Athlone, Ireland. Each IP carton will contain 18 AP01 overwrapped pouches, each pouch containing two ampoules. Each ampoule will contain 4 mL AP01 12.5 mg/mL formulation, which is a 50 mg dose. The 50 mg once daily inhaled dose cohort will use one IP carton every 4 weeks (1/2 pouch per day; 1 ampoule per once daily dose). The 100 mg twice daily inhaled dose cohort will use four IP cartons every 4 weeks (2 pouches per day; 2 ampoules per twice daily dose). Details of IP distribution will be outlined in the clinical study manual.

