### 11.2.3 Missing Data

Due to the COVID-19 pandemic, which occurred while the study was actively enrolling, additional strategies are included for handling missing data. Missing values will not be imputed for data displayed in summary tables. For patients with missing data due to death, remaining FVC values will be imputed as a sensitivity analysis using a lower value of FVC than the patient's last observed value. Because home spirometry data collection continues when COVID-19 prevented in-clinic visits, home spirometry FVC will be used to inform missing office spirometry data handling for reasons other than early terminations. Full details of imputation methods will be included in the SAP.

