For the sensitivity analyses of the primary efficacy endpoint, two different imputation strategies will be used to address missing in-clinic spirometry data used in the calculation of the change in absolute FVC % predicted from Baseline to Week 24. In both imputation strategies, missing data for early terminations other than deaths will be imputed for all visits following termination by assuming the average change at each visit calculated for all patients on the same cohort with FVC % predicted data available at that visit. For patients with missing data due to death, the remaining FVC % predicted values will be imputed as 30%.

For the second imputation strategy, in addition to imputing missing data due to early termination, home spirometry data will be used to replace missing in-clinic data using the following algorithm:

- Flag any biologically implausible home spirometry records for exclusion from analysis defined to be PFT measurements where the corresponding FVC % predicted value is <10 or >136.
- If home spirometry is available within the first two weeks following first dose of study drug, use it to calculate changes from baseline for home spirometry data.
- If home spirometry is not available within the first two weeks following first dose of study drug, use the patient's home spirometry data to fit a linear regression and the estimated intercept as a baseline for home spirometry data.

This document is confidential.

Statistical Analysis PlanSponsor: Avalyn Pharma, Inc.; Protocol No.: AP01-002

- Calculate all changes from baseline possible for a patient based on home spirometry data.
- Using any home spirometry data collected within the mapping window for a scheduled visit, create a pseudo office observation as the average of these home spirometry changes from baseline.
- Insert pseudo office observations for missed visits, setting the weeks of the observation to be the target weeks for that visit.

The primary variable will also be summarized by treatment group with descriptive statistics for the following subgroups: FVC (FVC % predicted ≤ 65 , $65 < \text{FVC \% predicted} < 80$, and FVC % predicted ≥ 80 at Baseline); region (Asia-Pacific and Europe); age at screening ($>$ Median level vs. \leq Median level); sex (Male and Female); baseline DLCO % predicted ($>$ Median level vs. \leq Median level) and baseline progression-related biomarkers (CXCL13, CCL18, MMP3) each categorized as $>$ Median level vs. \leq Median level.

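### Both sensitivity imputations give non-death dropouts their cohort's average FVC change, so they cannot show bias from patients withdrawn for decline, and they understate the error

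*SAP*

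**What the plan says.** The primary efficacy analysis (SAP 8.1) is a mixed-model slope in the per-protocol set. It imputes nothing and takes only patients with three or more FVC readings after baseline. The full analysis set is named for the first sensitivity analysis.

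Two imputation strategies follow, with a common rule for early terminations other than deaths: missing values are "imputed for all visits following termination by assuming the average change at each visit calculated for all patients on the same cohort", the average being taken over those with a reading at that visit. SAP 8.1 does not define cohort. Protocol 8.3.5 uses the word for a dose arm ("The 50 mg once daily inhaled dose cohort will use one IP carton every 4 weeks"), and I read it that way.

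The second strategy adds home readings for missed clinic visits. Protocol 11.2.3 restricts that use: "home spirometry FVC will be used to inform missing office spirometry data handling for reasons other than early terminations".

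For deaths, the SAP states that "the remaining FVC % predicted values will be imputed as 30"% predicted. Protocol 11.2.3 calls for imputation "using a lower value of FVC than the patient's last observed value". SAP section 12, on changes from the protocol, lists only the added full analysis set.

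Protocol 5.6 allows withdrawal in Part A when, in the investigator's opinion, "the patient is failing the study drug for lack of efficacy, as evidenced by an excessive decline of FVC". Protocol 5.3 also directs discontinuation in Part A when the investigator judges that oral antifibrotic treatment is needed.

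**The concern.** A missing-data sensitivity analysis should ask how the result changes if those who left did worse than those who stayed. Here withdrawal can follow directly from the outcome, yet every non-death dropout is assumed to have changed, after leaving, by the average of patients still observed. No multiple imputation, variance correction, delta shift or tipping point is specified in either document.

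Two consequences follow. Bias from these dropouts cannot appear, because the rule assumes it away. And filled-in values that sit exactly on the mean enter the model as if they were data, so the standard error is too small. A reader could take agreement with the primary result as evidence of robustness that was never tested. Comparing the regimens to guide later studies is a stated objective (Protocol section 2), so that reassurance could carry weight.

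**Working it through.** **Inputs.** SD 4.5, 50 patients per arm and a two-sided 95% interval come from Protocol 11.1. The documents give no dropout rate, so I assume 10%, 20% and 30%. I read the average change as mean change from baseline.

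**The plan's own figure.** 1.96 × 4.5/√50 = 1.247, which reproduces the stated 1.25.

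**Week 24 mean, closed form.** Let d be the dropout fraction and n_obs = 50(1 − d).

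- Point estimate: [n_obs·m + (50 − n_obs)·m]/50 = m, so the imputed mean equals the observed-case mean m.
- Half-width from observed patients: 1.96 × 4.5/√n_obs.
- SD after imputation: 4.5 × √[(n_obs − 1)/49]. Half-width after imputation: 1.96 × that SD/√50.
- Coverage: 2Φ(1.96 × ratio of half-widths) − 1.

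| Dropout | n_obs | Observed half-width | Imputed SD | Imputed half-width | Ratio | Coverage |
|---|---|---|---|---|---|---|
| 10% | 45 | 1.32 | 4.26 | 1.18 | 0.90 | 92% |
| 20% | 40 | 1.40 | 4.01 | 1.11 | 0.80 | 88% |
| 30% | 35 | 1.49 | 3.75 | 1.04 | 0.70 | 83% |

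All three imputed half-widths are narrower than the 1.25 planned with complete data.

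**Bias that stays hidden at Week 24.** If dropouts would have ended worse than the others by D points (assumed), the bias is d × D. For D = 3, 5 and 10 it is 0.3, 0.5 and 1.0 at 10% dropout, and 0.6, 1.0 and 2.0 at 20%. For scale, the oral pirfenidone trial cited in Protocol 11.1 had an active–placebo gap of 3.9 − 1.5 = 2.4.

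**Slope model, simulated.** The planned estimator is a slope, so I also ran 1,000 trials per scenario: one arm of 50, true change −1.5, slope SD 3.9, residual SD 2.2 (total about √(3.9² + 2.2²) = 4.5 at Week 24), dropout after one to four post-baseline visits, no deaths and no covariates.

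| Dropout, random | Imputed: model SE | Imputed: true SD of estimate | Imputed coverage | Primary-rule coverage |
|---|---|---|---|---|
| 10% | 0.554 | 0.600 | 92.3% | 94.7% |
| 20% | 0.522 | 0.627 | 89.6% | 95.2% |
| 30% | 0.491 | 0.658 | 84.5% | 95.5% |

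When faster decliners were made more likely to leave (20% dropout, mean true slope of leavers −5.17), the primary rule gave −0.93 and the imputed analysis −0.71, against a truth of −1.50. Coverage was 83% and 60%. The imputed result lies further from the truth, in the favourable direction.

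**Deaths.** Entry requires at least 40% predicted at Screening and a relative fall under 10% by Day 1 (Protocol 5.1), so baseline exceeds 40 × 0.9 = 36%. Imputing 30% is then a loss of more than 6 points from baseline. But a patient last seen at 27% is raised by 30 − 27 = 3 points, and one last seen at exactly 30% gets an equal value, not a lower one.

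**The case against.** A reader might infer that these analyses can only repeat the primary result. The documents do not support that. The full analysis set is named for the first sensitivity analysis. Patients with fewer than three readings may enter if imputed values count. Missed visits may be filled from home data. The death value is also a heavy penalty: with an assumed baseline of 70% and an arm mean of −1.5, one death in 50 shifts the Week 24 mean by (−40 + 1.5)/50 = −0.77.

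A reader might also infer that imputation leaves the planned estimate unchanged. The exact identity, and the standard-error ratio of about 1 − d, belong to a raw Week 24 mean. The slope can move, and its standard-error ratio was milder: 0.554/0.600 = 0.92 at 10% and 0.522/0.627 = 0.83 at 20%.

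Nor is a withdrawn patient's observed decline erased. Only visits after termination are imputed, and SAP 6.4 maps the termination visit to the nearest visit or analyses it by date.

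If average change means visit-to-visit increments, the return to the mean is softer. The rule would still be a single fixed imputation that assumes leavers decline like stayers.

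Finally, the primary objective is safety and tolerability, the documents plan no formal hypothesis tests (although SAP section 8 lists Wald tests against external references), and the Part B dose decision of 12 October 2020 preceded SAP 3.0 of 15 July 2021. These points limit the consequences. They do not repair the rule for non-death terminations.

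**Conclusion.** The concern holds for early terminations other than deaths, in both strategies. The rule cannot show bias from patients withdrawn for decline, may shift the slope favourably, and understates the error. Nominal 95% coverage for a Week 24 mean is about 92% at 10% dropout and 88% at 20%, and about 90% at 20% in the slope simulation with random dropout. Dropout rates, the deficits of leavers and the split of variance between slope and residual are assumptions. The direction of the standard-error result does not depend on them, but the sizes do.

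This should be fixed, but it is confined to supportive efficacy analyses. The primary model does not impute, so its standard error is untouched by this rule.

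On deaths, a reader might infer that the 30% rule can score a death as an improvement. It cannot do so on the endpoint, which is change from baseline. The conflict with the protocol is real but narrow: it arises only for a patient last seen at or below 30%.

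**What to change.** In SAP 8.1, for both strategies:

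- Replace the cohort-average fill with multiple imputation within arm, using each patient's baseline and all observed FVC, including the termination visit, and combine the results by Rubin's rules. State whether imputed values count towards the three-reading minimum.
- Add a delta or tipping-point analysis for non-death early terminations. Worsen the imputed values in steps over a prespecified range (for example up to 10 points at Week 24, the largest deficit worked above) and report where the conclusion changes. This step does the real testing, because multiple imputation alone still assumes that dropout is explained by the observed data.
- Reconcile the death rule with Protocol 11.2.3 so that the imputed value is strictly below the last observed one. One way is 30% or, if the last value is 30% or less, a prespecified amount below it. Taking the lower of 30% and the last value is not enough, because it only ties with the last value when that is 30% or less.
- List these changes in SAP section 12.

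The cost is SAP wording, modest programming and somewhat wider intervals.
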